## **Compliance**

Study drug compliance will be summarized for each treatment group for the FAS population. The compliance is defined as the number of tablets/capsules taken (i.e., the difference between the number of tablets/capsules dispensed and the number of tablets/capsules returned) divided by the number of tablets/capsules that should have been taken during the treatment period. Compliance with each study drug will be calculated for each subject and summarized with the mean, median, standard deviation, minimum, and maximum.

## **7.0 Demographics, Baseline Characteristics, Medical History, and Prior/Concomitant Medications**

Demographics, baseline or disease characteristics, medical history, and prior and concomitant medications will be summarized for the FAS overall and by treatment group. Categorical variables will be summarized with the number and percentage of subjects; percentages will be calculated based on the number of non-missing observations. Continuous variables will be summarized with descriptive statistics (number of non-missing observations, mean and standard deviation, median, minimum and maximum).

### **7.1 Demographics and Baseline Characteristics**

The following demographic and baseline characteristics, as measured at baseline of the Study M16-063 study, will be summarized.

#### **Demographic Characteristics**

- Age (years)
- Age category [18 – < 40 years old, 40 – < 65 years old, ≥ 65 years old]
- Sex [male/female]
- Race [White, Black or African American, American Indian or Alaska Native, Native Hawaiian or Other Pacific Islander, Asian, Other]

- Ethnicity [Hispanic/Latino, Non-Hispanic/Latino]
- Geographic region (North America, South/Central America, Western Europe, Eastern Europe, Asia, Other)
- Weight (kg)
- Weight Categories (< 60 kg, ≥ 60 kg)
- Height (cm)
- Body Mass Index (BMI) (kg/m^2)
- Body Mass Index (BMI) Category (kg/m^2) (BMI < 25 vs BMI ≥ 25)

#### **RA Medical History and Characteristics**

- Duration of RA Symptoms in years
- Duration of RA Diagnosis in years
- Duration of RA Diagnosis Categories (< 5 year or ≥ 5 year)
- Prior exposure to bDMARDs (failed 1 or 2 biologics with the same mechanism of action; failed ≥ 3 biologics with the same mechanism of action and/or ≥ 2 biologics with multiple mechanisms of action)
- Number of prior bDMARD received (1, 2, 3, ≥ 4)
- Concomitant csDMARDs at baseline (MTX alone, MTX and other csDMARDs, csDMARDs other than MTX)

#### **ACR and/or DAS Components at Baseline**

- Tender joint count (TJC68) defined as the number of tender joints out of 68 assessed joints
- Swollen joint count (SJC66) defined as the number of swollen joints out of 66 assessed joints
- Tender joint count (TJC28) defined as the number of tender joints out of 28 assessed joints used for DAS28 calculation
- Swollen joint count (SJC28) defined as the number of swollen joints out of 28 assessed joints used for DAS28 calculation

- Physician's global assessment of disease activity (mm on a 100-mm horizontal visual analogue scale [VAS])
- Patient's assessment of pain within last week (mm on a 100-mm horizontal (VAS))
- Patient's global assessment of disease activity within last 24 hours (mm on a 100-mm horizontal VAS)
- Health Assessment Questionnaire Disability Index of the (HAQ – DI) (range: 0 to 3)
- High sensitivity C-reactive protein (hsCRP) (mg/L)
- Erythrocyte sedimentation rate (ESR) (mm/hr)

#### **Other Baseline RA Disease Characteristics**

- Morning stiffness (severity and duration)
- Anti-cyclic citrullinated peptide (Anti-CCP) (units)
- Anti-CCP status: Positive or Negative
- Rheumatoid Factor (RF) (units)
- Rheumatoid Factor (RF) status: Positive or Negative
- Percentage of subjects on oral steroid at baseline
- Oral steroid dose (prednisone equivalent) at baseline
- DAS28 [ESR]
- DAS28 [CRP]
- CDAI
- DAS28 [ESR] Categories:
  - a. DAS28 [ESR] > 5.1 (High Disease Activity)
  - b. DAS28 [ESR] ≤ 5.1
- DAS28 [CRP] Categories:
  - a. DAS28 [CRP] > 5.1 (High Disease Activity)
  - b. DAS28 [CRP] ≤ 5.1
- CDAI categories:

- a. CDAI > 22 (High Disease Activity)
- b. CDAI ≤ 22

### **Clinical Tests at Screening**

- Chest x-ray
- Tuberculin PPD skin test, QuantiFERON TB Gold test
- Serum pregnancy test

### **Immunization History**

- BCG immunization
- Herpes Zoster immunization
- Hepatitis B immunization

### **Tobacco/Nicotine and Alcohol Use**

- Tobacco/Nicotine Use (current, former, never, or unknown)
- Alcohol Use (current, former, never, or unknown)

## **7.2 Medical History**

Medical history data will be coded using the Medical Dictionary for Regulatory Activities (MedDRA). The actual version of the MedDRA coding dictionary will be noted in the statistical tables and clinical study report. Medical history data will be summarized and presented for the FAS population using body systems and conditions/diagnoses as captured on the CRF. The body systems will be presented in alphabetical order and the conditions/diagnoses will be presented in alphabetical order within each body system. The number and percentage of subjects with a condition/diagnosis will be summarized for each treatment group as well as overall. Subjects reporting more than one condition/diagnosis within a body system will be counted only once for that body system. No statistical comparison will be performed for medical history reporting.

### **7.3 Prior and Concomitant Medications**

Prior and concomitant medications will be summarized by each treatment group as well as overall for the FAS. Prior medications are those medications taken prior to the first dose of study drug. This includes medications with a start date before the first study drug administration date, regardless of the end date of these medications. Medications taken on the day of the first dose of study drug are not counted as prior medications. Concomitant medications are those medications, other than study drug, taken after the first dose of study drug and within 1 day of the last dose of study drug. This includes medications with a start date between first study drug administration and last study drug administration + 1 day, as well as, medications with a start date prior to first dose of study drug and which are ongoing after first dose of study drug. Medications taken on the day of the first dose of study drug are counted as concomitant medications.

The number and percentage of subjects who received a prior medication and the number and percentage of subjects who received a concomitant medication will be tabulated separately by the generic name assigned by the most current version of the World Health Organization (WHO) Drug Dictionary.

## **8.0 Efficacy Analyses**

### **8.1 General Considerations**

Analysis of efficacy endpoints will be conducted on the FAS.

For all efficacy endpoints, the descriptive statistics will be provided by treatment group. The statistics include number of observations, mean, standard deviation, minimum, median, and maximum for continuous variables; and number and percentage of subjects for categorical variables.

The analysis treatment groups will be described as follows indicating from Study M16-063 to extension Study M16-763:

- Group 1: ABBV-599 to ABBV-599

- Group 2: ABBV-105 60 to ABBV-105 60 mg
- Group 3: ABBV-105 20 to ABBV-105 20 mg
- Group 4: ABBV-105 5 to ABBV-105 5 mg, and
- Group 5: Upadacitinib to Upadacitinib
- Group 6: Placebo to ABBV-599
- Group 7: All ABBV-599 (Group 1 and 6)

"Baseline" refers to the last non-missing observation before the first administration of study drug in Study M16-063 or randomization in Study M16-063 if no study drug is given.

## **8.2 Handling of Missing Data**

The analysis will be based on As Observed data, and no imputation will be conducted.

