5.5 Withdrawal of Subjects and Discontinuation of Study

A subject may voluntarily withdraw or be withdrawn from the study at any time for reasons including, but not limited to, the following:

- Clinically significant abnormal laboratory results or AEs, which rule out continuation of the study drug, as determined by the investigator or the AbbVie Therapeutic Area Medical Director.
- Serious infections (e.g., sepsis) that cannot be adequately controlled within 2 weeks by anti-infective treatment or would put the subject at risk for continued participation in the trial as determined by the Investigator.

- The investigator believes it is in the best interest of the subject.
- The subject requests withdrawal from the study.
- Eligibility criteria violation was noted after the subject started study drug and continuation of the study drug would place the subject at risk.
- Introduction of prohibited medications or dosages and continuation of the study drug would place the subject at risk.
- Subject is non-compliant with tuberculosis (TB) prophylaxis (if applicable) or develops active TB at any time during the study.
- The subject becomes pregnant while on study drug.
- Malignancy, except for localized NMSC or carcinoma in-situ of the cervix.
- Subject is significantly noncompliant with study procedures, which would put the subject at risk for continued participation in the trial.
- Subject develops a gastrointestinal perforation.

In addition, the following discontinuation criteria also apply:

- Subjects not responding to therapy can discontinue study drug (or withdraw from study) at any time for any reason during the study in order to receive standard of care.
- Subjects who demonstrate worsening of joint count (SJC and/or TJC) at 2 consecutive visits (scheduled or unscheduled) should be discontinued from study drug and treated with standard of care at the discretion of the clinician.
- Starting at the Week 18 visit (after the Week 18 assessments have been performed) and at visits thereafter, subjects who fail to achieve at least 20% improvement in TJC and SJC should be discontinued.

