- Starting at the Week 18 visit (after the Week 18 assessments have been performed) and at visits thereafter, subjects who fail to achieve $CDAI \leq 10$ should have background medication(s) adjusted or initiated (i.e., initiation of or change in corticosteroids, NSAIDs, acetaminophen or adding or increasing doses in csDMARDs [restricted to oral or parenteral MTX, sulfasalazine, hydroxychloroquine, chloroquine and leflunomide except the combination of MTX and leflunomide is allowed as per local label]).
- Starting at the Week 18 visit (after Week 18 assessments have been performed) and at visits thereafter, intra-articular, intramuscular, intravenous, trigger point or tender point, intra-bursa, and intra-tendon sheath injections of corticosteroids, dosage and frequency per standard of care are allowed. For the analysis of the TJC and SJC, injected joints will be considered "not assessable" for 3 months from the time of the intra-articular injection.
- Starting at the Week 24 visit and at visits thereafter, subjects achieving 20% improvement in TJC and SJC but not achieving $CDAI \leq 10$ should be considered for discontinuation to standard of care at the discretion of the clinician.

Subjects who prematurely discontinue study drug should complete a Premature Discontinuation (PD) Visit as soon as possible, preferably within 2 weeks of discontinuation. See Section 5.6 for information regarding early discontinuation.

For subjects to be considered lost to follow-up, reasonable attempts must be made to obtain information on the subject's final status. At a minimum, 2 telephone calls must be made and 1 certified letter must be sent and documented in the subject's source documentation.

AbbVie may terminate this study prematurely, either in its entirety or at any site. The investigator may also stop the study at his/her site if he/she has safety concerns. If AbbVie terminates the study for safety reasons, AbbVie will promptly notify the investigator.

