5.6 Follow-Up for Subject Withdrawal from Study

To minimize missing data for efficacy and safety assessments, subjects who prematurely discontinue study drug treatment should continue to be followed for all regularly scheduled visits, unless subjects have decided to discontinue the study participation entirely (withdrawal of informed consent). Subjects should be advised on the continued scientific importance of their data even if they discontinue treatment with study drug early.

Following discontinuation of study drug, the subject should be treated in accordance with the investigator's best clinical judgment irrespective of whether the subject decides to continue participation in the study. In addition, all future rescue- and efficacy-driven discontinuation criteria no longer apply. This includes 20% TJC/SJC calculations at Weeks 12 through 24, Weeks 36 through 40 and Week 48 and thereafter, as well as CDAI calculation at Week 26, if applicable. If at any point a subject no longer wants to provide assessments (withdrawal of informed consent) following discontinuation of study drug, a second PD visit is not required.

If a subject prematurely discontinues study participation (withdrawal of informed consent), the procedures outlined for the PD visit should be completed as soon as possible, preferably within 2 weeks. In addition, if subject is willing, a 30-day follow-up phone call after the last dose of study drug may be completed to ensure all treatment-emergent AEs/SAEs have been resolved.

All attempts must be made to determine the date of the last study drug dose and the primary reason for discontinuation of study drug or study participation. The information will be recorded on the appropriate electronic case report form (eCRF) page. However, these procedures should not interfere with the initiation of any new treatments or therapeutic modalities that the Investigator feels are necessary to treat the subject's condition. Following discontinuation of study drug, the subject should be treated in accordance with the Investigator's best clinical judgment irrespective of whether the subject decides to continue participation in the study.

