7.3 Statistical Analyses for Efficacy

Analysis of efficacy endpoints will be conducted on the FAS based on treatments as randomized for Study M16-063. The analysis will be based on As Observed data, and no imputation will be conducted. The analysis treatment groups will be described as follows indicating from Study M16-063 to extension Study M16-763:

- Group 1: ABBV-599 to ABBV-599
- Group 2: ABBV-105 60 to 105 60 mg
- Group 3: ABBV-105 20 to 105 20 mg
- Group 4: ABBV-105 5 to 105 5 mg
- Group 5: Upadacitinib 15 to Upadacitinib 15 mg, and
- Group 6: Placebo to ABBV-599
- Group 7: All ABBV-599 (Group 1 and 6)

The baseline for all efficacy analyses in this study will be the baseline in Study M16-063.

There is no primary efficacy endpoint and no formal statistical tests will be applied. Only descriptive statistics will be used for all efficacy endpoints. Descriptive statistics will be provided for each treatment group for all visits. These include the number of observations, mean with 95% confidence interval, standard deviation, median, minimum and maximum for continuous endpoints (or the change from baseline measurements), and frequencies and percentages with 95% confidence interval for binary endpoints.

No missing data imputation will be applied. All efficacy analyses will be based on As Observed analysis, and thus a subject who does not have an evaluation at the primary analysis time point will not be included.

Details on efficacy analyses are provided in the SAP.

Sample Size Estimation

This is the LTE study for Study M16-063. All eligible subjects who completed Study M16-063 will be enrolled in this study if the subject signs and dates the informed consent. Based on discontinuation criteria mandating efficacy, it is estimated that 20 - 60% of subjects (i.e., between 40 and 120 subjects) will ultimately complete the LTE.

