## **8.4 Secondary Efficacy Analyses**

Descriptive statistics will be provided for each treatment group for all visits. These include the number of observations, mean with 95% confidence interval, standard deviation, median, minimum and maximum for continuous endpoints; and frequencies and percentages with 95% confidence interval using Wilson score for binary endpoints.

No missing data imputation will be applied. All efficacy analyses will be based on As Observed (AO) analysis, and thus a subject who does not have an evaluation at the primary analysis time point will not be included.

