## **8.5 Additional Efficacy Analyses**

No additional efficacy analyses are planned.

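### Efficacy is summarised only As Observed, so late visits mix on-drug and off-drug response and cannot alone show that efficacy is maintained on treatment

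*SAP*

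**What the plan says.** SAP 8.2 sets the data rule for all efficacy endpoints: "The analysis will be based on As Observed data, and no imputation will be conducted". SAP 8.4 and Protocol 7.3 repeat it and give a single reason for leaving a subject out: "thus a subject who does not have an evaluation at the primary analysis time point will not be included". Study-drug status at the visit is not mentioned. The FAS needs only one dose in the extension, and subjects are grouped as randomized in M16-063 (SAP 4.0). SAP 8.5 adds: "No additional efficacy analyses are planned". SAP 8.6 plans no subgroup analyses.

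Protocol 5.6 asks that "subjects who prematurely discontinue study drug treatment should continue to be followed for all regularly scheduled visits", unless they withdraw consent. After stopping, they are treated by the investigator's "best clinical judgment irrespective of whether the subject decides to continue participation in the study".

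Protocol 5.5 ties stopping to response. From Week 18, "subjects who fail to achieve at least 20% improvement in TJC and SJC should be discontinued". From Week 24, those who meet the joint-count threshold but not CDAI ≤ 10 "should be considered for discontinuation to standard of care at the discretion of the clinician". SAP 2.4 expects 20-60% of subjects, 40 to 120 people, to complete, and attributes this to the efficacy-based discontinuation criteria.

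The clinical hypothesis (SAP 2.1) is that safety and efficacy persist with longer treatment. Protocol 4.2 makes the main comparison each arm against its own M16-063 profile.

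**The concern.** The extension asks whether response lasts while patients keep taking the drug. The tables planned to answer this count everyone assessed at a visit, whatever they are then taking. Those who leave study drug are mainly those who respond poorly, and most or many entrants are expected to leave.

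A flat As Observed curve over Weeks 18 to 60 therefore has at least three possible explanations: study drug kept working, poor responders stopped attending, or poor responders improved on other treatment. A falling curve is just as unclear. The safety side has a rule of this kind, since SAP 9.2.1 counts adverse events up to 30 days after the last dose. Efficacy has no equivalent rule and no planned display that separates the two states.

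**Working it through.** **Reproducing the plan's figure.** 40 / 0.20 = 200 and 120 / 0.60 = 200. Both ends of SAP 2.4 imply about 200 entrants, so 200 − 120 = 80 to 200 − 40 = 160 are expected not to complete.

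**Off-drug share of Week 60 values.** Let c be the share completing on drug. I take this as 0.20 to 0.60, which assumes that completing the extension means completing on drug; the documents do not say so. Let f be the share of stoppers who still attend. This is also an assumption, so the full range is shown.

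Off-drug share = f(1 − c) / [c + f(1 − c)]

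- f = 1 (everyone attends, as Protocol 5.6 asks): 0.80/1.00 = 80% at c = 0.20; 0.40/1.00 = 40% at c = 0.60.
- f = 0.5: 0.40/0.60 = 67%; 0.20/0.80 = 25%.
- f = 0 (a bound only, contrary to the intent of 5.6): 0% at both.

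**What this can do to a response rate.** Assume 60% response on drug, and 20%, 40% or 60% off drug. No document gives these rates. As Observed rate = 0.60 × (1 − share) + off-drug rate × share.

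| c | f | off-drug 20% | off-drug 40% | off-drug 60% |
|---|---|---|---|---|
| 0.20 | 1 | 28% | 44% | 60% |
| 0.20 | 0.5 | 33% | 47% | 60% |
| 0.60 | 1 | 44% | 52% | 60% |
| 0.60 | 0.5 | 50% | 55% | 60% |
| either | 0 | 60% | 60% | 60% |

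On-drug responders over the full FAS would be 0.60 × 0.20 = 12% to 0.60 × 0.60 = 36%. With on-drug response held at 60% throughout, the reported figure can thus run from 28% to 60% As Observed.

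**What the planned tables already show.** SAP 6.0 tabulates exposure in M16-763 at ≥ 42, 85, 127, 168, 252 and 336 days. Divided by 7, these are 6, about 12, about 18, 24, 36 and 48 weeks. Counted from entry at Week 12 (Protocol Appendix D), they fall at Weeks 18, 24, 30, 36, 48 and 60. SAP 5.0 gives treatment completion and reasons for stopping by group, and SAP 8.4 gives the number of observations at each visit. Together these let a reader approximate how many are on drug at each visit. The approximation is loose: visits have a ±7-day window, exposure runs from first to last dose regardless of interruptions, exposure is summarised on the Safety Analysis Set (grouped as treated), and missed assessments blur the subtraction. No table shows response by drug status. SAP 7.3 counts a medication as concomitant only up to 1 day after the last dose, so treatment started later is not tabulated either.

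**The case against.** The best defence is that the plan is complete on its own terms. As Observed on the FAS, grouped as randomized, is a legitimate treatment-policy summary. With lack of an evaluation as the only exclusion, values after stopping are included on a plain reading. This stands: a reader might infer that the SAP leaves inclusion open, but the texts together point one way and lack only an explicit sentence.

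A reader might also infer that the number on drug at each visit is hidden. SAP 5.0 and 6.0 do not support that, because it can be roughly recovered. Nor do the documents support saying that As Observed results will be biased upward. The direction depends on attendance and on response to other treatment, and the documents give neither.

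A further objection is that an on-drug summary does not isolate study-drug effect. This also stands. On-drug subjects are selected by the stopping rules, and from Week 18 those above CDAI 10 should have background medication adjusted or started while on study drug (Protocol 5.4 and 5.5). A full-FAS non-response table has the opposite fault: it falls as subjects stop even if response among those on drug is unchanged (60% becoming 12-36% in the example above). No single table answers the question, which is the reason to show them side by side.

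Finally, efficacy is descriptive, with no primary endpoint and no hypothesis test (SAP 3.1 and 12.0). No error rate or formal conclusion is at risk.

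**Conclusion.** The point holds as a limit on interpretation. Followed as written, the As Observed tables pool study-drug response with response to other care or, if stoppers do not attend, describe a group selected for response. Either way they cannot by themselves address efficacy maintained with prolonged treatment. With 80 to 160 of about 200 not expected to complete, the off-drug part of Week 60 data could be 40-80% under full attendance, 25-67% under half and 0% under none.

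Only the completion range comes from the documents. Attendance, response rates and the meaning of completing are assumptions, so these figures show what is possible and do not predict a size. It should be fixed because it is cheap and because, in a descriptive study, the tables are the result.

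**What to change.** Leave Protocol 5.5 unchanged and keep As Observed. Before database lock, in SAP 8.2 and 8.4:

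- **(a)** State that values after the last dose of study drug are included in As Observed.
- **(b)** At each visit show n on and n off study drug by group, with an on-drug summary of binary and continuous endpoints beside As Observed. Define on-drug status, including how interruptions count. Note that on-drug subjects are selected and may have had background medication adjusted from Week 18, so the summary does not isolate study-drug effect.
- **(c)** For binary endpoints add a supplementary table on the full FAS denominator that counts study-drug discontinuation or a missing assessment as non-response, labelled conservative. This is a form of imputation, so the no-imputation statements in Protocol 7.3 and SAP 8.2 and 8.4 must be reconciled to apply to the As Observed analysis.

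The cost is a few extra tables from data already collected, a wording change in both documents, and less favourable rates that will need explaining. On-drug groups will be small. If the six groups are equal (an assumption), 40/6 to 120/6 gives about 7 to 20 completers each. Wilson 95% intervals would then be as wide as 49-97% for 6/7 and 58-92% for 16/20.
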